**Sample Size Determination:**

Both primary effectiveness and primary safety endpoint analyses will be conducted on the MITT population, where subjects with missing data at the time of endpoint analysis will be imputed as last observation carried forward (LOCF). Hence all subjects in the MITT population with post-procedure data are deemed to be evaluable for the purpose of MITT analyses. Subjects who receive the device but in whom there is no post-procedure data will be treated as failures for the primary effectiveness analysis; subjects who do not receive the device because of treatment failure due to reasons associated with the device will also be treated as failures. Subjects with no post-procedure endpoint data upon which to base a LOCF imputation will be excluded from the primary safety endpoint analyses; it is anticipated that fewer than 7% of MITT subjects will be excluded from either primary effectiveness or primary safety endpoint analyses. Subjects who are enrolled but who are found to be ineligible for treatment with ENTERPRISE at the time of the pre-procedure angiogram will be replaced. Subjects in whom treatment with ENTERPRISE is attempted but who discontinue study participation prematurely will not be replaced.

The study design is a group sequential design, wherein after N=160 subjects have been enrolled, treated, and followed for a minimum of 6 months post-procedure, an interim analysis will be conducted to determine whether or not to terminate the study early for futility or tentative success.

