The study will terminate early for tentative success if the unadjusted 2-sided normal approximation p-value for testing the primary effectiveness endpoint (RCAO vs. the PG of 35%) is less than 0.031, and will terminate early for futility if this p-value is greater than 0.358. If the stopping rule is met for the trial to stop early for tentative success, a final confirmatory analysis will be conducted when all subjects have reached 12 months post-procedure; a p-value threshold of 0.031 will be used for this final confirmatory analysis. If neither of these interim analysis criteria for stopping the trial early is met, or if the confirmatory analysis for early success is not satisfied, then enrollment will commence until a total sample of N=320 subjects have been enrolled (including the original N=160), and all subjects will be followed for a minimum of 12 months post-procedure at which time the final primary endpoint analysis will be conducted. In this final primary endpoint analysis, the study will be deemed to be successful if the unadjusted 2-sided normal approximation p-value for testing the primary effectiveness endpoint (RCAO vs. the PG of 35%) is less than 0.031.

The statistical power to stop early for success at the interim analysis is approximately 79% if the true RCAO is 47% in the general population and there are at least 150 evaluable MITT subjects (with post-procedure data) for this interim analysis. The statistical power at the final endpoint (if the study continues to full enrollment) is 87.7% if the rate of complete occlusion in the general population is 44% and there are 300 evaluable MITT subjects (with post-procedure data) for this final analysis. With the group-sequential design of this study and the specified interim and final analyses for the primary endpoint, including the sample sizes at which analyses will be conducted and the p-value thresholds for determining study success in the respective analyses, the overall probability of a Type 1 error in this study ( $\alpha$ , 2-sided) is maintained below 0.05.

There are two primary safety endpoints with formal hypotheses that will be tested, and the following are estimates of statistical power for each of these respective endpoints at the time of the interim analysis. For each respective endpoint, the purpose of the hypothesis test is to ensure that the 2-sided 95% upper confidence limit for the estimate is less than a stated performance goal for the

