The technical success measures were also assessed using the angiographic core lab. Successful intracranial device placement (defined as stable CODMAN ENTERPRISE placement with complete coverage of the aneurysm neck and parent artery patency) was achieved in 85.7% of the cases. Satisfactory coil mass position (defined as CODMAN ENTERPRISE maintains coil position within the sac with parent artery patency as defined angiographically) was 83.5% immediately post-procedure and 83.3% at six months. Complete aneurysm occlusion was achieved in 20.2% of cases immediately post-procedure and in 58.2% of the subjects with 6 months follow-up.

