It is anticipated that fewer than 15% of entered subjects will be unevaluable at the 12 month follow-up visit due to loss to follow-up and/or missing primary angiographic occlusion or safety data. However, subjects with missing data at the time of endpoint analysis will have primary effectiveness and primary safety endpoint data imputed as last observation carried forward (LOCF). Subjects who receive the device but in whom there is no post-procedure data will be treated as failures for the primary effectiveness analysis; subjects who do not receive the device because of treatment failure due to reasons associated with the device will also be treated as failures. Subjects with no post-procedure endpoint data upon which to base a LOCF imputation will be excluded from the primary safety endpoint analyses; it is anticipated that fewer than 7% of MITT subjects will be excluded from either primary effectiveness or primary safety endpoint analyses. Thus, although the primary endpoint analyses will be in the Modified Intent to Treat (MITT) population for primary effectiveness and safety endpoints, up to 320 subjects will be enrolled to achieve approximately 300 subjects with post-procedure data in the MITT population. A group sequential design will be employed in which one primary endpoint interim analysis will be conducted after N=160 subjects have been enrolled and followed through 6 months post-procedure, to determine if the study should stop early for futility or tentative success; it is anticipated that there will be at least N=150 subjects with post-procedure data in the MITT population for this analysis. If the stopping rule is met for the trial to stop early for tentative success, a final confirmatory analysis will be conducted when all subjects have reached 12 months post-procedure. If the trial is not terminated early for futility or tentative success, then enrollment will continue up to the full enrollment sample size of N=320.

Patients who experience an AE of Special Interest and who have an MRS >2 at any clinical evaluation will be followed through 24 months post-procedure.

An independent core laboratory will perform the quantitative analysis for the primary and secondary effectiveness endpoints, as well as for subjects where the 12 month angiogram is an endpoint assessment. A medical monitor will adjudicate the relationship of AEs to the device, procedure, and/or underlying disease in accordance with the definitions specified within this protocol.

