
## 3.2 Study Endpoints

### 3.2.1 Primary Effectiveness Endpoint

- The primary effectiveness endpoint is the Rate of Complete Aneurysm Occlusion (RCAO) at 12 months post-procedure according to the Raymond Scale as assessed by the Independent Core Laboratory.

Complete aneurysm occlusion is defined as an aneurysm in which a score of 1 (complete obliteration) is achieved on the Raymond Scale at the relevant post-procedure angiogram, without additional procedures for treatment of the aneurysm since the index procedure. Subjects who are retreated (retreatment includes staged procedures) prior to the 12 month post-procedure follow-up visit will be considered not to have achieved complete aneurysm occlusion for the purpose of the primary endpoint analysis.

The primary endpoint analysis will be to demonstrate that the RCAO is significantly greater than a performance goal (PG) of 35%. The primary endpoint null and alternative hypotheses are:

Null hypothesis  $H_0$ :  $\text{RCAO} \leq 35\%$

Alternative hypothesis  $H_A$ :  $\text{RCAO} > 35\%$

This analysis will be conducted on the modified intent-to-treat (MITT) population of subjects (subjects who are found to be eligible for treatment with ENTEPRISE at the time of the pre-procedure angiographic assessment, and in whom treatment is attempted). A supportive analysis will be conducted on the PP population.

**Note:** The study will be deemed to be a success if this primary efficacy endpoint null hypothesis (on the MITT population with data from all sites combined) is rejected in favor of the alternative hypothesis.

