## 9.5 Handling of Missing Data

Primary effectiveness and primary safety endpoint analyses will be conducted on the modified intent-to-treat (MITT) population, where subjects with missing data at the time of endpoint analysis will be imputed as last observation carried forward (LOCF); see Section 9.8 for analysis set definitions. Note that the immediate post-procedure evaluation will be utilized in this LOCF methodology if this is the last observation on file. MITT subjects who receive the device but in whom there is no post-procedure data will be treated as failures for the purpose of the primary effectiveness endpoint analysis; these subjects will be excluded from all other endpoint analyses. Subjects who do not receive the device because of treatment failure due to reasons associated with the device will also be treated as failures for the primary effectiveness endpoint analysis; these subjects will be excluded from all other endpoint analyses. MITT subjects who do not receive the device because of an intra-operative surgeon decision based on patient anatomy (e.g. vessel tortuosity) will be treated as missing (and not as failures) in all endpoint analyses, including the primary effectiveness and primary safety endpoint analysis.

All subjects who have died prior to an evaluation will have a mRS score of 6 imputed for that time point for analysis purposes.

All other analyses based upon MITT or PP population data will be based upon actual data, with no data imputation.

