#### **4: Dataset Flow Diagram for Enrolled Subjects**

True RAO in the Patient Population	Overall Power to demonstrate Primary Efficacy (at Interim or Full Enrollment)	Probability of Stopping Early for Success (Interim Analysis)	Probability of Study Success at Full Enrollment if Not Stopped at Interim Analysis	Probability of Stopping Early for Futility (Interim Analysis)
0.35	2.70%	1.40%	2.90%	60.80%
0.37	10.60%	4.60%	12.40%	54.80%
0.4	41.40%	18.00%	40.90%	32.20%
0.42	68.10%	33.90%	62.60%	17.60%
0.43	79.10%	43.30%	72.10%	12.10%
0.44	87.70%	53.20%	80.50%	8.00%
0.45	93.30%	62.70%	86.90%	4.90%
0.46	96.80%	71.70%	91.80%	2.90%
0.47	98.60%	79.30%	95.00%	1.60%
0.5	99.90%	93.90%	99.30%	0.20%

An estimate of the overall Type 1 error rate for this study design can be seen in the first row of this table, where the true RAO in the patient population is equal to the performance goal of 35% for the Primary Efficacy Endpoint; this estimated Type 1 error rate is 2.7% (2-sided), which is below 5%. An estimate of overall statistical power is 87.7% if the true RAO is 44% in the patient population, and the likelihood of stopping early for tentative study success is approximately 79.3% if the RAO in the patient population is 47%. The likelihood of stopping early for futility is approximately 54.8% if the RAO in the patient population is 37%.

There are two primary and secondary safety endpoints with formal hypotheses that will be tested, and the following are estimates of statistical power for each of these respective endpoints at the time of the interim analysis. For each respective endpoint, the purpose of the hypothesis test is to ensure that the 2-sided 95% upper confidence limit for the estimate is less than a stated performance goal for the endpoint. The performance goal, expected outcome, and estimated statistical power based upon a sample size of N=150 evaluable subjects (with post-procedure data) are provided for each respective endpoint.

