10.6 Handling of Missing Data

Unless stated otherwise, missing data will not be imputed, percentages will be based on non-missing data.

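### Carrying the end-of-procedure angiogram forward to 12 months tends to favour the device on in-stent stenosis and lowers effectiveness power; the protocol should bar it and the SAP should define who is counted for stenosis.

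*Protocol*

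**What the plan says.** Protocol 9.5 imputes missing primary effectiveness and safety data by LOCF in the MITT population, and allows the acute image as the carried value: "Note that the immediate post-procedure evaluation will be utilized in this LOCF methodology if this is the last observation on file". The synopsis (Sample Size Determination) draws the consequence: "Hence all subjects in the MITT population with post-procedure data are deemed to be evaluable for the purpose of MITT analyses". Protocol 3.1 expects that "fewer than 15% of entered subjects will be unevaluable at the 12 month follow-up visit", without saying how many of these would have a 6-month angiogram.

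The effectiveness test asks whether "RCAO is significantly greater than a performance goal (PG) of 35"%. The text below the operating-characteristics table in Protocol 9.9 states: "An estimate of overall statistical power is 87.7% if the true RAO is 44% in the patient population". For stenosis, Protocol 9.7 requires the upper 2-sided 95% normal-approximation limit to lie below 15%.

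On how far occlusion changes after the procedure, Protocol 1.3.4 reports from the sponsor's registry: "Complete aneurysm occlusion was achieved in 20.2% of cases immediately post-procedure and in 58.2% of the subjects with 6 months follow-up".

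The SAP takes another course. Its section 10.6 says "missing data will not be imputed, percentages will be based on non-missing data" unless stated otherwise. Section 10.4.1.1 excludes subjects with no 12-month Raymond score, and 10.4.1.2 excludes subjects with missing stenosis data. Sections 6, 10.4 and 10.5 cancel the hypothesis tests and the interim analysis because the study ended early for low enrollment. No reason is given for dropping LOCF.

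**The concern.** Carry-forward assumes that the last image is a fair stand-in for the 12-month image. An image taken before the end of the procedure is not. Stenosis counted through 12 months has had almost no time to appear, so an early loss tends to enter as a subject without an event. That favours the device on a primary safety endpoint. Occlusion moves the other way: the registry went from 20.2% to 58.2% in six months, so an early loss is mostly entered as not occluded. The power calculation nevertheless treats all 150 or 300 subjects as having a true 12-month rate of 44%.

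A second problem lies in the SAP and still matters for the final report. Section 10.4.1.2 counts stenosis up to and including 12 months but does not define missing data. SAP section 4 treats images outside the visit windows as missing and keeps only the most recent image within a window. The 6-month window ends at Day 240 and the 12-month window starts at Day 270, so an image on Days 241 to 269 falls in neither. A stenosis that was actually seen could therefore be dropped, while a clean acute image might still place a subject in the denominator.

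**Working it through.** **Inputs.** RCAO goal 35%, assumed rate 44%, 150 and 300 evaluable subjects, 2-sided p<0.031 at each look, futility at p>0.358 (synopsis: "is less than 0.031, and will terminate early for futility if this p-value is greater than 0.358"). Acute occlusion 20.2% (Protocol 1.3.4). Stenosis goal 15% with a normal-approximation limit (Protocol 9.7). Let f be the share of analysed subjects whose carried value is the acute image. The documents do not give f; 0 to 15% is the assumed range, and its top equates all missing 12-month data with acute-only data.

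**Step 1: reproduce the plan.** The z-test uses the null variance 0.35 × 0.65 / n, with critical value 2.157. Success needs at least 66 of 150 or 123 of 300. The exact two-look binomial probability at 44% is 87.6% when futility is not enforced (stated 87.7%) and 84.4% if futility is binding. Without futility the type I error is 2.7% (stated 2.7%), and early success at 47% is 79.3% (stated 79.3%).

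**Step 2: RCAO with acute carry-forward.** Analysed rate = 0.44(1 − f) + 0.202f. For f=5%: 0.418 + 0.0101 = 42.8%. The type I error column uses 0.35(1 − f) + 0.202f.

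| f | Analysed rate at true 44% | Power, no futility | Power, binding futility | Type I error, no futility |
|---|---|---|---|---|
| 0 | 44.0% | 87.6% | 84.4% | 2.7% |
| 2% | 43.5% | 84.0% | 80.5% | 2.1% |
| 5% | 42.8% | 77.3% | 73.5% | 1.5% |
| 10% | 41.6% | 63.2% | 59.4% | 0.8% |
| 15% | 40.4% | 47.2% | 43.8% | 0.4% |

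If 15% lack a 12-month image but some of them have a 6-month image, the loss shrinks. With half having one, power without futility is 70.7% if the carried 6-month rate is 44%, and 81.8% if it is the registry's 58.2%. With two thirds, it is 77.3% and 89.2%.

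**Step 3: stenosis at a true 15%.** The Wald limit passes up to 15 of 150: 0.100 + 1.96 × √(0.1 × 0.9 / 150) = 14.8%, while 16 gives 15.6%. It passes up to 34 of 300 (limit 14.9%; 35 gives 15.3%). With carried subjects assumed event-free, the analysed rate is 0.15(1 − f), and the chance of passing is the binomial probability of at most 15 or 34 events.

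| f | Analysed rate | Pass, n=150 | Pass, n=300 |
|---|---|---|---|
| 0 | 15.00% | 4.9% | 4.1% |
| 5% | 14.25% | 8.0% | 8.3% |
| 10% | 13.50% | 12.6% | 15.5% |
| 15% | 12.75% | 18.9% | 26.2% |

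If 3% of carried subjects show acute stenosis (assumed), the f=15% row becomes 14.9% and 19.4%. The 4.9% and 4.1% at f=0 already exceed the nominal 2.5%; that part comes from the Wald limit, not from LOCF.

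**Step 4: exclude instead.** If missing subjects are left out and missingness is unrelated to outcome, 5%, 10% and 15% missing leave 142/285, 135/270 and 128/255 subjects. Power at 44% without futility is about 85%, 83% and 82%. The stenosis error stays at 4.3–4.9% at interim size and 4.0–4.1% at final size.

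**The case against.** The strongest reply is that the consequences have lapsed. The SAP excludes missing data, runs no tests and no interim analysis, and offers its intervals without inferential intent. No pass/fail decision on stenosis remains, and no power claim has to be met. This stands. A reader might infer that the final stenosis rate will be biased by carry-forward or judged at an inflated error rate; the SAP's own rules do not support that.

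A reader might also infer that the rule abolishes the 87.7% power. The documents do not support that either. The 15% in Protocol 3.1 is an upper limit on everyone unevaluable at 12 months, including subjects whose 6-month angiogram would be carried. The acute-only share is not stated, so 47% is a worst case.

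It is equally tempting to treat carried subjects as certainly stenosis-free. No acute stenosis rate is given, and Protocol 3.2.4.6 makes acute stenosis an endpoint, so zero is an assumption.

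For effectiveness the rule is conservative: the type I error falls, and no false claim of success follows from it.

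Finally, scoring acute-only subjects as not occluded might look like the natural remedy, but it would cost more power than the rule it replaces: 65.6%, 36.1% and 13.3% at 5%, 10% and 15%. It belongs in a sensitivity analysis.

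**Conclusion.** The concern holds as a fault in the protocol design and as a gap in the SAP's stenosis definition.

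- **Stenosis:** acute carry-forward tends to favour the device. Its size depends on an unstated acute-only share and an unstated acute stenosis rate; over the assumed 5% to 15% range, the chance of wrongly passing roughly doubles at the low end and reaches four to six times its starting level at the high end.
- **RCAO:** the stated power makes no allowance for acute carry-forward. The first few percent carried cost about two points of power each. The loss is smaller where missing subjects have 6-month images.
- **Final report:** none of these error or power figures applies to it. What remains live is that the two documents prescribe different numerators and denominators for the same primary endpoints, with the change unexplained, and that SAP 10.4.1.2 read with SAP section 4 could drop an observed stenosis or count a clean acute image as a 12-month result.

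**What to change.** **Protocol 9.5.** Bar the immediate post-procedure image from carry-forward for stenosis and RCAO. Treat subjects with no later image as missing, in line with the SAP, and score their RCAO as not occluded only in a sensitivity analysis. State beside the 87.7% that it assumes no acute carry-forward.

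**SAP 10.4.1.2.** Count as an event any in-stent stenosis read by the core laboratory on any angiogram, scheduled or unscheduled, from the procedure to Day 450. Say that this overrides the window and most-recent-value rules of SAP section 4. Take as denominator the subjects with an event or an angiogram in the 12-month window; a clean acute image alone never qualifies. Alongside it, show the rate with subjects having a 6-month or later image as denominator. Record that the SAP departs from the protocol's LOCF, and why.

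**Cost.** Wording in the missing-data sections, one programming rule and one extra line in a table. A few subjects leave the stenosis denominator. The main rate leans slightly upward, because a subject with only a clean 6-month image is dropped while one with stenosis at 6 months is kept; the second denominator shows by how much.

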## 9.6 Primary and Secondary Endpoints

### Primary Endpoint

#### **Efficacy:**

The primary effectiveness endpoint is the rate of complete aneurysm occlusion (RCAO) at 12 months post-procedure according to the Raymond Scale as assessed by the Independent Core Laboratory.

Complete aneurysm occlusion is defined as an aneurysm in which a score of 1 (complete obliteration) is achieved on the Raymond Scale at the relevant post-procedure angiogram, without additional procedures for treatment of the aneurysm since the index procedure. Subjects who are retreated (retreatment includes staged procedures) prior to the 12 month post-procedure follow-up visit will be considered not to have achieved complete aneurysm occlusion for the purpose of the primary endpoint analysis.

#### **Safety:**

There are two primary safety endpoints: The incidence of Major Ipsilateral Stroke and/or Death at 12 months post-procedure and the incidence of In-stent stenosis at 12 months post-procedure.

#### **Incidence of Major Ipsilateral Stroke and/or Death:**

Major ipsilateral stroke and/or death will be evaluated from the start of the index procedure until completion of the 12 month follow-up. A major ipsilateral stroke is defined as a new neurological event which is ipsilateral and in the vascular distribution territory of the stenting procedure and that results in an increase of  $\geq 4$  on the National Institute of Health Stroke Scale (NIHSS) as compared to baseline and persists for greater than 24 hours.

#### **Incidence of In-Stent Stenosis:**

In-stent stenosis at or prior to 12 months post-procedure will be assessed angiographically. In-stent stenosis is defined as greater than 50% narrowing of the vessel within the ENTERPRISE stent or within 10 mm of either end of the stent.

### **Secondary Endpoints**

#### **Secondary Effectiveness Endpoints:**

**Procedure Success:** Procedure Success is defined as the percentage of aneurysms in which coil mass position is maintained within the sac with parent artery patency, without additional procedures for treatment of the aneurysm since the index procedure. Procedure success will be summarized immediately post-treatment (acute), and at the 6 and 12 month follow-up assessments.

**Acute and 6 Month Complete Aneurysm Occlusion as per the Raymond Scale:** The percentage of aneurysms in which a score of 1 (complete obliteration) is achieved on the Raymond Scale immediately post-procedure (acute) and at the 6 month follow-up angiographic assessments, respectively, will be evaluated.

**Complete/Partial Aneurysm Occlusion as per the Raymond Scale:** The percentage of aneurysms in which a score of 1 (complete obliteration) or 2 (residual neck) is achieved on the Raymond Scale immediately post-procedure (acute), and at the 6, and 12 month follow-up angiographic assessments will be evaluated.

**Percent Aneurysm Occlusion:** The percentage of aneurysms with occlusion of 100%, 90%-99%, 70-89%, 50-69%, 25-49%, or <25% occlusion in accordance with Consensus Grades 0-5, respectively, will be summarized immediately post-procedure (acute), and at 6 and 12 month follow-up, respectively.

